#### Manual observation under microscope

- Examine slide under microscope (20x objective, 10x eyepiece)
- Identify as positive sickling test (SCD or SCT) if greater than 25% of the red blood cells appear sickled or deformed (Figure 1 shows sickling in an SCT individual)

#### Automated scanning using microscope

- Place microscope slide in slide holder of microscope unit (Octopi microscope)
- Identify the edges of the field of view for scanning
- Run program to automatically scan and capture images in the computer (translation of the stage and slide enabled by motors)
- Save images for machine learning algorithm (training/testing data set)

**Figure 1** | Blood film containing SCT blood mixed with 2% sodium metabisulphite, showing minimal sickle cells around 10 minutes after sample preparation (left) and increased number of sickle cells around 1.5 hours after sample preparation (right); 40x objective, 10x eyepiece

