## 1.5 Conventional screening and diagnosis

The following techniques have been commonly used to detect hemoglobin S (HbS) related to SCD or SCT.

**Sickling test**: The presence of hemoglobin S can be demonstrated in a sickling test, where red blood cells change their shape from round bi-concave shape to sickled shape, under conditions of hypoxia or deoxygenation. When a drop of blood is sealed (using petroleum jelly/paraffin wax mixture or nail lacquer) between a glass slide and a cover slip, the metabolic activity of white blood cells causes deoxygenation, which induces sickling after a few hours, if HbS is present. The deoxygenation can be accelerated by adding a reducing agent such as sodium metabisulphite or sodium dithionite. Sickling can be induced using a reducing agent within 30 minutes to an hour for SCD and SCT, and the changes in morphology of red blood cells can be observed under a microscope, to distinguish SCD and SCT individuals from healthy participants [2], [13]. The sensitivity of the sickling test ranges from 65% [14] to 97.3% [15] and the specificity ranges from 96% [14] to 99.6% [15]. The sickling test, which is relatively inexpensive, was predominantly used as a screening test for HbS, but has mostly been replaced by the solubility test.

**HbS solubility test**: The solubility test relies on the principle that hemoglobin S, when deoxygenated, is insoluble in a high molarity phosphate buffer, which forms crystals that refract light and causes the solution to turn turbid [2]. Sickle solubility tests provide positive results for cases of SCD and SCT beyond early infancy – for early infancy (infants less than 6 months) the percentage of HbS can be below 20%, which could result in false negative tests [13]. The sickle solubility test, whether positive, negative or ambiguous, should be followed up by a confirmatory test, such as hemoglobin electrophoresis. The follow up tests are required to confirm the presence of HbS, distinguish SCT from SCD, or identify false negative cases due to low HbS concentration or technical error [13]. For rapid results or for emergency cases, the sickle solubility test can be combined with a blood count and a blood film analysis to distinguish SCT from SCD with reasonable accuracy. The sensitivity of the solubility test ranges from 45% [14] to 99% [15] and the specificity ranges from 90% [14] to 99.9% [15].

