Currently, machine learning has been implemented in peripheral blood smears but not on deoxygenated blood films prepared during sickling tests, where much more sickle cells appear on both SCT and SCD blood samples than on a blood smear. The conventional sickling test can classify SCT/SCD patients from healthy participants, but is not typically used to distinguish between SCT and SCD under manual observation. D'Costa *et al.* [26] recently slightly modified the sickling test by using two different concentrations of sodium metabisulphite with diluted blood on a microfluidic chamber, and were able to distinguish between SCD and SCT using image analysis. They also found that the distribution of morphology of sickle cells under hypoxia was different for blood from SCD and SCT patients. This was attributed to differences in HbS polymerization depending on the concentration of hemoglobin S and the rate of deoxygenation, which has also been observed earlier [40]. The differences in morphology between SCD and SCT can potentially be used to classify SCD, SCT and healthy participants using the sickling test, combined with machine learning, which is one of the aims of this study.

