## Reagent (2% sodium metabisulphite) preparation

- Add 0.2 g of sodium metabisulphite to 10 mL of distilled water in a vial/container
- Mix or stir till dissolved
- Prepare fresh every time (and use within 3 hours)

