#### Microscope slide preparation

[figure not shown]
- Mix 1 drop of blood with 1 drop of 2% sodium metabisulphite on a microscope slide
- Add cover slip
- Incubate at room temperature for 30 minutes

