# 8.0 Study Schedule

**Screening**: Potential participants will be approached by investigators/study delegates who will explain the rationale, goals and risks and benefits of study participation. If subjects acknowledge and confirm voluntary participation in the study, then the informed consent form will be signed and the participant's enrolment will commence at the time of next blood collection.

**Blood Draws**: Participants who have been consented within the past 30 days will arrive at either Mount Sagarmatha Polyclinic for drawing blood as part of their routine visit (e.g. for SCD or SCT participants) or a visit for the study (e.g. for normal participants).

**Tests**: The HPLC tests will be performed at Mount Sagarmatha Polyclinic. The low-cost tests will be performed at the hematology lab at the hospital/clinic. Images of blood films for the sickling tests will be taken at the hematology lab using the Octopi microscope assembly.

**Analyses**: The machine learning algorithms will be trained and tested after collecting the images for blood films of the sickling test. The analyses will be performed at UBC. The performance of the algorithms will be tested with the data collected during the study, and at the end of the study (after completion of all tests). The statistical analyses will be performed after all the data has been collected.

**Reporting results**: After completing the study, the results will be published either as a separate report or together with the results from the Vancouver study.

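### Scan time after the 30-minute incubation is neither capped nor logged, and the data split is by image, so slide-age or session features could inflate the automated sickling test's accuracy

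*Combined protocol and SAP*

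**What the plan says.** **Time dependence.** The Figure 1 caption, in section 7.5.1 under Automated scanning using microscope, describes an SCT blood film "showing minimal sickle cells around 10 minutes after sample preparation (left" and an "increased number of sickle cells around 1.5 hours after sample preparation". Section 1.5 states: "Sickling can be induced using a reducing agent within 30 minutes to an hour for SCD and SCT". Section 1.6 (Machine Learning) attributes the SCD/SCT shape differences to HbS polymerization that varies with "the concentration of hemoglobin S and the rate of deoxygenation".

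**Timing rules.** Under Microscope slide preparation the instruction is "Incubate at room temperature for 30 minutes". This comes before both the manual and the automated reading. The scanning step itself is "Run program to automatically scan and capture images in the computer", with no latest start, scan duration or time log. The reagent rule, "Prepare fresh every time (and use within 3 hours", limits the reagent and not the slide. The participant code in section 7.4 carries the collection site and date and a serial number or collection time, but no preparation or scan time.

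**Data split and sessions.** Section 7.8 divides the acquired images about 80/10/10 and mentions neither participant nor session. Section 8.0 has blood drawn at a routine visit (SCD and SCT given as examples) or at "a visit for the study (e.g. for normal participants". All films are imaged in one laboratory. Nothing mixes the groups within imaging sessions.

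**The concern.** Hypothesis 3 asks the network to separate SCD, SCT and healthy blood by cell morphology with sensitivity above 90%. Hypothesis 2 compares the automated test with the conventional sickling and solubility tests. The amount of sickling on an SCT slide changes with time since preparation. If that time varies freely and is not recorded, it adds variation to the very feature being classified, and nobody can later adjust for it or show that it was harmless.

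The split makes this worse. If images of one slide, or of slides made in one session, fall in both the training and the test set, the network can be rewarded for recognizing features that those images share by circumstance, such as slide age, reagent batch or imaging conditions. Test accuracy would then overstate performance on a new participant on a new day, which is what the long-term aim of screening in Nepal depends on.

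Manual reading is exposed too. Its positive call depends on more than 25% of red cells being sickled or deformed, so a systematic difference in slide age between the two readings would make the sickling part of Hypothesis 2 an uneven comparison.

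**Working it through.** **1. The plan's own figure.** Sections 6.3 and 7.2.1 give six groups of 20: 6 × 20 = 120, as stated. The concern disputes no figure in the plan.

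**2. The timing statements side by side.**
- Figure 1 time points: about 10 minutes (minimal sickling) and about 1.5 hours = 90 minutes (more sickling).
- Earliest reading: 30 minutes. The 10-minute state is therefore never read.
- Induction time in section 1.5: 30 to 60 minutes. The earliest reading falls at the start of this range, so up to 60 − 30 = 30 minutes of it may lie after the first permitted reading.
- Latest reading: not stated. Slide age at scan: not recorded.

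Change after 30 minutes is therefore possible on the protocol's own account. How much changes between 30 and 90 minutes is not given.

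**3. What an image-level split allows.** Assume that images are allocated at random, 80% to training, and that each slide yields *m* images. The protocol speaks of images in the plural but gives no number. The chance that a test image has at least one image of the same slide in training is about 1 − 0.2^(m−1):
- m = 1: 1 − 1 = 0%
- m = 2: 1 − 0.2 = 80%
- m = 3: 1 − 0.04 = 96%

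Each slide carries one phenotype, so any feature that identifies the slide also identifies the label. This shows how readily information could be shared. It does not show how much the network would use.

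**4. What visit type alone could do (illustration).** Let *q* be the assumed share of each group seen at its typical visit. The rule calls HbAA at a study visit and HbAS at a routine visit, and sees nothing of the blood.
- HbAA against HbAS and HbSS: sensitivity = specificity = q, that is 50% at q = 0.5, 80% at 0.8 and 100% at 1.0.
- Three classes of 20 each: accuracy = (q + q + 0)/3, that is 33% at q = 0.5, 53% at 0.8 and 67% at 1.0. SCD and SCT share a visit type, so visit type cannot separate them.
- HbS detection over all six groups, calling routine visits positive and assuming that all three HbS groups attend routine visits: sensitivity = q. If both β-thalassemia groups without HbS also attend routine visits, specificity = (20q + 40(1 − q))/60, which at q = 1 is 20/60 = 33%. If they attend study visits, specificity = q, which at q = 1 is 100%. The documents do not say which visit these groups attend.

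The 67% ceiling applies to visit type only. It does not bound what slide-level or session-level features could contribute under step 3.

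**The case against.** The case against has several sound parts.

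- **Figure 1 does not cover the reading period.** It contrasts 10 with 90 minutes, and the incubation rules out the first. This stands: the change within the permitted period is unknown.
- **A reader might infer that a late SCT slide would pass for an early SCD slide.** The documents do not support this. Figure 1 shows SCT blood only, and section 1.6 says that the shapes differ between SCD and SCT, not only the number of sickled cells. The rate of deoxygenation is also not the same thing as elapsed time.
- **A reader might infer that healthy slides will be marked by slide age or session.** Nothing ties slide age to group. The only age-dependent feature described is sickling, which needs HbS. The visit types are examples that concern blood draws, and all imaging takes place in one laboratory. Fresh reagent is a standardizing measure.
- **A reader might infer that scans always follow manual reads, which would favour the automated test.** That rests on the order in which the subsections are printed. The protocol states neither the sequence nor whether both readings use the same slide. The solubility comparison in Hypothesis 2 would be unaffected in any case.

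The gap survives these points. The scan time has a floor but no ceiling or record, and section 7.8 as written does not keep related images together. Neither depends on visit type or on the order of reading.

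**Conclusion.** The point holds as an uncontrolled risk to Hypotheses 2 and 3, not as a demonstrated bias. The documents establish that sickling in SCT blood rises with time since preparation, that scanning after 30 minutes has no upper limit or logged slide age, and that the split is described for images. From these it follows that slide-age or session features shared by training and test images could make the automated test look more accurate than it is.

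No size can be put on this from the documents. The visit-type percentages rest on an assumed *q* and largely return that input. At most, visit type could help to separate healthy from SCD/SCT participants. The shared-slide percentages rest on random allocation of images and an assumed number per slide. The documents do not support the stronger conclusion that slide age or session will stand in for phenotype.

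The change is still worth making before data collection, because slide ages that are not logged may not be recoverable afterwards.

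**What to change.** 1. State a window after the 30-minute incubation within which every scan must start, and log preparation, manual-read and scan times for each slide.
2. Alternate the order of manual reading and scanning, or use two slides from the same tube, so that Hypothesis 2 compares slides of similar age.
3. Mix patient and healthy slides within imaging sessions where feasible.
4. In section 7.8, keep all images of a participant, and where feasible of a session, in one data split.
5. Report a sensitivity analysis that excludes out-of-window scans, and a check of whether slide age or session alone predicts phenotype.

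**Cost.** Logging the times needs no extra blood. Scheduling becomes slightly tighter, and mixing groups depends partly on when patients make routine visits. Splits become less flexible: a 10% test set by participant is about 0.1 × 120 = 12 people, or 0.1 × 20 = 2 per group, so grouping by session as well may not always be possible. That is why items 3 and 4 ask for session-level control only where feasible.

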#### 7.5.2 HbS Solubility Test

The methods used for the HbS Solubility test are as follows:

#### Reagent preparation

- Add reagents in the following proportion (and in the order specified) [2]:
  - 1 liter of water
  - o 215 g of anhydrous dipotassium hydrogen phosphate K2HPO4
  - o 169 g of anhydrous potassium dihydrogen phosphate KH2PO4
  - o 5 g of sodium dithionite Na2S2O4
  - o 1 g of saponin
- The prepared solution is stable for 7 days in a refrigerator

#### Testing procedure [2]

- Add 2 mL of reagent to three test tubes using a pipette
- Let reagent warm to room temperature
- From EDTA container, add 10 µL of packed cells to one tube
- Create positive control using 10 μL of packed cells from known SCT patient (HbAS) to second tube
- Create negative control using 10 μL of packed cells from a known normal subject (HbAA) to third tube
- Mix the blood-reagent mixture well and let stand for 5 minutes
- Ensure that the blood-reagent mixture is light pink or red (a light orange color appears if the reagent has deteriorated)
- Place tubes 2.5 cm in front of a white sheet with narrow black lines
- Compare the turbidity with positive and negative controls
- The test is positive if the solution is turbid (black lines are not observed through the solution), and is similar to the positive control, as shown in Figure 2
- The test is negative if the solution is clear (black lines are observed through the solution), and is similar to the negative control, as shown in Figure 2

[figure not shown]

Figure 2 | Results of the HbS solubility test showing (from left to right) a positive control (turbid), a negative control (clear), a positive test (turbid) and a negative test (clear) [13]

#### 7.5.2 HemoTypeSC

# **Testing procedure** [46]

- Add six drops of water to test vial, using dropper pipette (Step 1 in Figure 3)
- Obtain around 1 microliter of blood sample, using fingerprick, heel-stick or EDTA tube
- Place white pad of the blood sampling device on blood sample until it absorbs a droplet of blood (Step 2 in Figure 3)
- Place blood sampling device into test vial, and swirl to mix till blood has transferred to the test vial (Step 3 in Figure 3)
- Ensure that the water has turned pink or light-red in color
- Leave the blood sampling device in the test vial
- Insert the HemoTypeSC test strip into the test vial, with the arrows pointing down (Step 4 in Figure 3)
- Wait for ten minutes (Step 5 in Figure 3)
- Remove the HemoTypeSC test strip and read the results, as shown in Figure 4

[figure not shown]

Figure 3 | Testing procedure of HemoTypeSC

[figure not shown]

Figure 4 | Results of HemoTypeSC test strip indicating all possible combinations [46]

#### 7.5.3 Sickle SCAN

#### **Testing procedure**

- Collect five microliters of blood, taken by fingerprick, heel-stick, or venipuncture, using the capillary sampler provided (Step 1 of Figure 5)
- Mix blood with buffer solution provided in the PreTreatment Module, to release hemoglobin by lysing red blood cells (Step 2 of Figure 5)
- Add five drops of treated sample from the PreTreatment Module into the sample inlet of the Sickle SCAN cartridge
- Wait for 5 minutes
- Read the results as shown in Figure 6

Figure 5 | Testing procedure of Sickle SCAN [47]

[figure not shown]

Figure 6 | Test results of Sickle SCAN showing Normal, SCT, SCD and HbSC disease cases [47]

#### 7.5.4 Gazelle Variant Test

### **Testing procedure** [48]

- Mix blood with marker fluid (Step 1 in Figure 7)
  - $\circ$  Pipette 40 µL of Gazelle Marker Fluid and 20 µL of blood into an Eppendorf tube and close the lid on the tube.
  - Vortex the solution for 20 seconds.
- Wet cartridge paper with buffer (Step 2 in Figure 7)
  - o Open an Hb Variant Cartridge from the Hb Variant Test Multipack.
  - Hold the cartridge at a 35-45° angle from horizontal. Hold the pipettor at 90° to the cartridge and in one smooth motion, slowly pipette 50 μL of Gazelle Buffer into the round hole next to the cartridge slot.
  - Insert the cartridge into the stamper stand with the cartridge's notched corner facing up.
  - Wait for 60 seconds
- Apply blood sample to the Cartridge (Step 3 in Figure 7)
  - Lay the cartridge flat with the slot side up. Place the stamper stand directly over the cartridge.
  - o Pipette 20 µL of the blood and marker fluid mixture onto a glass slide.
  - Gently touch the corner of a new stamper to the mixture until the stamper tip is filled from end to end.
  - Gently place the stamper with blood and marker fluid mixture into the slot on the stamper stand.
  - Place a finger on each side of the stamper stand and hold it down for five seconds.

# 1. Prepare Blood Sample and Vortex 40 μL 20 μL 20 SEC 1.3 MARKER FLUID PATIENT BLOOD 2. Wet Paper SIDE A NOTCH UP! μĹ SEC WET ENTIRE PAPER STAMPER STAND 3. Pipette Sample and Stamp DO NOT 20 µL IMMERSE! 3.3 SIDE A **GLASS SLIDE** BLOOD AND MARKER **COVER CARTRIDGE** WICK WITH STAMPER SEC PLACE STAMPER STAMP CARTRIDGE 4. Fill Wells and Start Test 200 μL SIDE B FILL WELLS PLACE CARTRIDGE START TEST

Figure 7 | Testing procedure of Gazelle Hb Variant [48]

- Fill wells and start test (Step 4 in Figure 7)
  - o Remove the stamper and stamper stand from the cartridge.
  - $_{\odot}$  Flip the cartridge over to SIDE B with the notched corner facing the user, and pipette 200  $\mu$ L Gazelle Buffer into the left well first
  - $\circ$  Pipette 200 µL of buffer into the right well. For best results, angle the pipette toward the center of the cartridge.
  - o Place the cartridge on the reader
- Close the lid and press START TEST on the touchscreen

#### 7.5.5 HPLC

HPLC will be performed using the same technique used for routine tests for patients at the hospital/clinic. Each test uses approximately 5  $\mu$ L of whole blood.

# 7.6 Equipment

#### 7.6.1 HPLC

The HPLC instrument at Mount Sagarmatha Polyclinic is the D10 System by Bio-Rad Laboratories. Quality control is performed prior to each run or with each new cartridge as per manufacturer's recommendations.

#### 7.6.2 Microscope

A low-cost automated microscope platform, Octopi (Open configurable high-throughput imaging platform for infectious disease diagnosis in the field), will also be used to capture images of blood films. A 20x magnification objective lens (infinity corrected) from Olympus will be used, along with a tube lens and a monochromatic camera. The microscope assembly will be equipped with motors for translation and autofocus. More details about Octopi (and related Squid) platforms can be found in https://doi.org/10.1101/684423 and https://doi.org/10.1101/2020.12.28.424613.

# 7.8 Neural Network Training and Testing

Data manipulation and analysis will be done through Python. All software to be utilized is opensource and does not have commercial implications. In order to optimize the screening algorithm, multiple neural network configurations will be tested and compared. All the models tested for classification will use existing pre-trained models that have applications in image classification. In each case, the acquired images will be split into three groups, consisting of training data (around 80%), validation data, (around 10%) and testing data (around 10%). The data will be used to train the neural network using a pre-trained supervised machine learning model, whereby the images are input and the parameters of the network are optimized to classify images by hemoglobin phenotype. The test data will test the performance of the trained network on images that have not been used for training. We will use the neural networks most commonly used for medical image classification, such as EfficientNet, ResNeXt, ResNet-50, DenseNet, and Xception. When possible, training will occur locally on the laboratory computer at UBC. For networks that require additional computing power, UBC ARC Sockeye or Compute Canada will be used.

All the machine learning algorithms will only include de-identified data, such as images of blood films and hemoglobin phenotype (such as sickle cell trait or HbAS). Personal identifying information, such as participant names, will not be associated with any of the data used for analysis or stored online.

Cloud computing facilities, such as those from Compute Canada, will be utilized to train and test machine learning algorithms on the final dataset of images. Compute Canada is a cloud computing service provided by Digital Research Alliance of Canada (the Alliance) to Canadian research institutions. The servers and clusters (e.g. Cedar cluster located in BC) will be accessed using Secure Shell Protocol (SSH). For the analysis (before sharing the data publicly), de-identified images may be stored securely in UBC servers or in servers for Compute Canada.

The de-identified data (such as images of blood films and associated de-identified data like hemoglobin phenotype) will be deposited in an online public repository, such as Federated Research Data Repository.

For this study, the machine learning algorithm will not be used to diagnose new patients, and the ground truth will be derived from results from the gold standard test (HPLC). The images of blood cells will be trained/tested using results from HPLC as the ground truth (e.g. diagnosis of sickle cell trait).

